1.0 INTRODUCTION AND BACKGROUND

In the process of degenerative disc disease (DDD), the intervertebral disc is often found to be the primary source of pain.¹⁻⁷ Spinal fusion procedures that stop motion at the disc are currently the preferred treatment for DDD. Posterior and posterolateral fusion procedures have been used, and fusion rates range from 46% to 100%.⁸⁻¹⁸ Fusion with internal spinal instrumentation has been shown to yield more reliable (80% to 90%) fusion rates.^{1, 19, 20}

Removal of the disc followed by an interbody fusion procedure is the most reliable procedure for treating a painful disc because it can restore tension to the annulus and further curtail motion.^{4, 21-26} A successful interbody fusion is more likely to result in a successful clinical outcome (pain reduction, function improvement).⁶ A bone graft placed in the intervertebral disc space has a potential mechanical advantage over posterior or posterolateral fusions by allowing restoration of disc space height, sagittal plane alignment, and weight bearing through the anterior column.^{19, 21-23, 27-29} The disc space provides a large surface area for fusion, and compressive loads applied to the graft stimulate osteogenesis and fusion.

The clinical outcomes of anterior and posterior interbody fusions are similar.^{19,30} An anterior interbody fusion allows a surgeon to avoid dissection of posterior paraspinal muscles and manipulation of the spinal cord and nerves. However, injury to iliac vessels and retrograde ejaculation has been reported.^{19, 31-34} Also, in many cases of degenerative disc disease, a decompression of the posterior neuroforamen is warranted, which would require a separate posterior procedure.

The posterior interbody fusion approach allows the surgeon to address both anterior and posterior pathology through the same incision. Using the posterior approach, bone grafts can be placed in the disc space via a translaminar or transforaminal approach. The transforaminal approach allows the surgeon to avoid excessive nerve root and /or thecal sac retraction, which can lead to neural injury and postoperative fibrosis, and avoid excessive removal of posterior structures, which would lead to gross instability of the motion segment.¹⁹

In 2001, over 122,469 lumbar fusions were performed nationwide for degenerative conditions.³⁵ By 2005, it was estimated this number had increased to more than 300,000 lumbar spine fusion being performed in the United States annually³⁶. Currently, industry research estimates that for 2014, approximately 75,000 minimally invasive posterior lumbar fusions performed domestically will utilize an interbody device with supplemental fixation.

For interbody fusion with posterior fixation, spine surgeons currently place structural intervertebral spacers into the interbody space. These spacers may be pre-shaped devices constructed of allograft (cortical bone dowels or femoral rings) or non-metallic, radiolucent materials (such as polyether ether ketone, PEEK), or metallic cage devices. Autogenous bone graft and blood components (marrow, blood) are often added.

Use of morselized bone graft in orthopedic procedures is desirable because morselized graft is more rapidly incorporated during the course of bone healing. If the morselized graft pack can be effectively contained in the interbody space, the graft material can function as a structural spacer to provide anterior column support. Contained graft material can be tightly packed within the mesh to increase the graft's compressive strength. Unlike pre-shaped cortical grafts, the morselized pack conforms intimately to the host bone at the surgical site, ensuring good vascularization potential and reducing the osteoblast jumping distance for osteogenesis. In addition, the solidly packed graft retains intra-pack porosity, ensuring an osteoconductive scaffold to facilitate vascular and bony ingrowth.

It would be desirable to minimize autograft use because of associated post-operative pain and morbidity, to optimize contact between allograft and host bone, and to permit the surgeon to place or construct an effective structural intervertebral spacer with only minimal neural retraction required.

The SIFS is intended to be used to contain the bone graft placed by spine surgeons into the interbody space to achieve spinal intervertebral body fusion. The SIFS mesh enables the use of morselized bone graft materials in spine fusion procedures instead of pre-shaped materials, such as solid allograft cortical bone dowels or femoral rings, or rigid synthetic materials such as PEEK or titanium.

In addition, the SIFS allows the surgeon to perform an interbody fusion through a small portal and to complete the entire fusion procedure from a posterior approach instead of a 360 degree anterior/posterior procedure, which is often the case with the use of cages. The minimal access portal utilized for the SIFS mesh filling allows the device to be placed via a unilateral transforaminal or translaminar approach, versus the often-used bilateral approach required for many cages and cortical spacers. This flexibility permits the surgeon to adapt the surgical approach to the local anatomy of the patient.

1.1 DEVICE DESCRIPTION

The Spineology Interbody Fusion System (SIFS) consists of two components; the SIFS mesh device and the SIFS instruments.

The Device – The SIFS mesh is a graft containment and reinforcement device. The SIFS mesh is filled *in situ* with bone graft. It is provided sterile and is a biocompatible, radiolucent, porous polyester mesh sack knitted from polyethylene terephthalate (PET) thread. PET material is widely used to make surgical sutures and meshes. The SIFS mesh device is pliable, conformable, and strong under tensile and burst forces as demonstrated through *in vitro* studies including axial compressive mechanical testing of the filled device's load-bearing capabilities and overall segmental strength. Beyond the mechanical testing, evaluation of the device was performed in an animal test model to further assess the biomechanical, radiographical and histological properties of the device. Human clinical outcomes

have also been investigated under IDE G030106. Refer to the SCOUT Investigational Plan for mechanical and biomechanical *in vitro* test protocols and results as well as *in vivo* outcomes.

The Instruments – Following conventional thorough discectomy, the SIFS instruments allow the surgeon to finish the preparation of a large area of the disc space through a small portal in the annulus, introduce the SIFS mesh in its undeployed state into the prepared fusion bed cavity, and fill the mesh with bone graft. The SIFS requires only minimal vascular and neural retraction during delivery of SIFS mesh and the graft material. Utilizing the device specific instruments, the SIFS mesh is deployed and filled. During the initial stages of mesh filling, the device expands and conforms to the cavity affording intimate graft apposition against the prepared vertebral endplates. The porosity of the mesh cage permits direct contact between the graft and the bleeding host bone at the mesh pores. As the density of contained graft increases within the mesh during the filling process, the graft may then distract the spinal segment. By nature of the flexible fabric design, SIFS mesh allows complete filling of the prepared site with graft material while minimizing the risk of graft extravasation into the surrounding area. Graft containment reinforces the granular bone pack, making it capable of bearing load and increasing segmental stability.

The SIFS received market clearance (K014200) on November 26, 2003 for containment of bone graft materials within the vertebral body. In the present investigation, the SIFS mesh is considered investigational, for the current cleared labeling does not identify use of the SIFS mesh in an interbody fusion application as a cleared indication.

1.2 INTENDED USE

The Spineology Interbody Fusion System is intended for use as an adjunct to fusion in instrumented lumbar fusion procedures for the treatment of degenerative disc disease. The SIFS mesh component is intended to maintain the relative position of bone graft material. The device is limited to use by or on the order of a physician.

1.3 INDICATIONS FOR USE

The Spineology Interbody Fusion System is indicated for use in an intervertebral body fusion at one level in the lumbar spine from L2 to S1, in skeletally mature patients with degenerative disc disease (DDD) with up to a Grade I spondylolisthesis at the involved level. In this investigation, DDD is defined as discogenic back pain with degeneration of the disc confirmed by patient history, examination and radiographic studies. These patients shall have undergone six (6) months of conservative (non-operative) treatment. The Spineology Interbody Fusion System with *G2 Dry Mix* allograft is intended for use with supplemental

posterior fixation systems cleared by FDA for use in the lumbar spine. It is designed for use with autograft as an adjunct to fusion.

Note: *G2 Dry Mix* is an allograft mixture available from the Musculoskeletal Transplant Foundation (MTF), Edison, NJ. *G2 Dry Mix* contains corticocancellous bone chips and demineralized bone matrix (DBM).

1.4 INSTRUCTIONS FOR USE

Following a thorough discectomy and adequate preparation of the vertebral body endplates, the SIFS mesh is deployed within the prepared disc space, utilizing the SIFS instruments. The SIFS mesh is primarily filled with rehydrated *G2 Dry Mix* (granular human tissue allograft mixture), augmented with autograft and bone marrow aspirate. The segmental construct is further stabilized with bilateral supplemental posterior fixation. Only investigators trained in the use of the Spineology Interbody Fusion System may utilize the investigational device. Refer to the SIFS Surgical Technique Manual (**Appendix I**) for complete instructions for use and implantation of the device.

1.5 CONTRAINDICATIONS AND CAUTIONS

Use of the SIFS mesh is contraindicated in individuals with a known sensitivity to PET.

G2 Dry Mix graft: Trace amounts of Gentamicin, Primaxin and Amphotericin B antibiotics may be present. Trace amounts of Polysorobate-80, Ethanol, Methanol, Isopropanol, Polyoxyethylene (10) Phenol Ether and Hydrogen Peroxide may be present. Caution should be exercised if the patient is allergic to any of these substances.

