4.0 SELECTION OF SUBJECTS

To participate in this clinical investigation, a subject shall meet the study entrance criteria. This means that at the time of screening, a subject shall meet all of the inclusion criteria and none of the exclusion criteria.

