4.1 INVESTIGATION POPULATION

Candidates for this investigation shall be skeletally mature, presenting with painful lumbar degenerative disc disease at a single level from L2 to S1. Subjects may have up to a Grade I spondylolisthesis at the index (involved) level. For this investigation, DDD is defined as discogenic back pain with degeneration of the disc confirmed by patient history, examination and radiographic studies. Study subjects shall present with low back pain. These subjects are to have been treated with conservative (non-surgical) measures for a minimum of six (6) months without achieving sufficient relief from their symptoms. The investigator is responsible for determining subject eligibility per the defined investigation inclusion and exclusion criteria.

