5.3 ASSESSMENTS AND PATIENT CARE

5.3.1 *Screening and Enrollment*

Prior to enrollment into this investigation, subjects shall be screened for potential inclusion. Subjects who undergo screening but do not meet the study entrance criteria are considered screen failures. Screen failures are documented on the Screening Log. Subjects meeting all study entrance criteria may be enrolled and treated. Enrolled subjects are to be followed in accordance with the study protocol through a maximum of 48-months postoperative (active visits through the 24 months postoperative; remote longer-term follow-up self-administered questionnaires at 36 months and 48 months post-op as necessary and appropriate until the last subject enrolled has achieved their final exam at 24-months postoperative). Once a subject has achieved their final assessment based on the above parameters, the subject's participation in this trial is complete.

5.3.2 *Study Interval Evaluations*

Intervals – Following enrollment into this investigation, subjects are followed periodically over time with pre-specified data being obtained at designated intervals. Subjects are actively assessed (i.e., includes physical examination and testing) prior to receiving the study treatment (baseline), through the surgical procedure and discharge from the hospital, at 6-weeks post-operative and at 3-, 6-, 12-, and 24-months post-operative. Beyond the above active assessment intervals performed in the health practitioner's setting, subjects shall undergo longer-term remote assessment in the form of completion of self-administered surveys/questionnaires. The longer-term patient survey/questionnaire forms shall be completed at the 36- and 48-month interval until the final study subject has achieved their 24-month study evaluation. **Table 1** indicates the subject evaluation time points and the correlating assessments to be performed at each study interval.

X-rays – Study radiographs shall be performed weightbearing (WB) and utilizing a magnification marker, allowing core lab assessments to adjust for magnification discrepancies and ensuring measurement accuracy over time.

The study specific magnification marker shall be provided by the sponsor to investigation sites. X-rays are performed at each active study visit through the 24-month interval.

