7.2 RISKS

7.2.1 SIFS Mesh Risks

The potential risks associated with the study device include but are not limited to:

- Mesh disruption (tear)
- Device migration
- Allergic reaction to PET

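### The mesh's only stated contraindication, known PET sensitivity, does not appear in the entrance criteria, so a patient who has it can satisfy all of them

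*Combined protocol and SAP*

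**What the plan says.** Section 1.1 describes the device as a "porous polyester mesh sack knitted from polyethylene terephthalate (PET) thread". Section 1.5 gives one contraindication for it: "Use of the SIFS mesh is contraindicated in individuals with a known sensitivity to PET". The same section treats trace substances in the allograft differently, as a caution only: "Caution should be exercised if the patient is allergic to any of these substances". Section 7.2.1 names three mesh risks, one of which is "Allergic reaction to PET".

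Entry is governed elsewhere. Section 4.0 sets the rule: "This means that at the time of screening, a subject shall meet all of the inclusion criteria and none of the exclusion criteria". Section 4.1 assigns the decision: "The investigator is responsible for determining subject eligibility per the defined investigation inclusion and exclusion criteria". Section 5.3.1 gives the consequence: "Subjects meeting all study entrance criteria may be enrolled and treated". Section 3.2.11 then states that all enrolled subjects are to be treated with the mesh, and 3.2.12 repeats this.

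Section 10.0 describes the Inclusion/Exclusion Entrance Checklist as the form for screening against the study entrance criteria.

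**The concern.** The sponsor identified a group of patients who should not receive this implant, and the part of the protocol that decides who enters does not mention them. The indications in 1.3 were turned into operating criteria in 4.2 and 4.3: single level, L2 to S1, skeletal maturity, up to Grade I spondylolisthesis, six months of conservative treatment. The contraindication in 1.5 was not, which looks like an oversight.

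The first thing at stake is subject safety at entry to a trial of an implant. There is a secondary link to the primary endpoint. Under 3.2.1 a subject fails the composite on a device-related serious adverse event at the index level. A serious reaction to the mesh, if adjudicated as device-related, would count against the device although it arose from an avoidable entry error.

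**Working it through.** No calculation in the plan bears on this point, so the check sets the passages side by side.

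1. **Is there a matching exclusion?** Section 4.3 has 15 top-level items: prior implant surgery at the index level, spondylolisthesis grade, symptomatic non-index disease, infection, malignancy, BMI, metabolic bone disease, interfering medication, substance disorder, other psychiatric diagnoses, Waddell signs, tobacco, prisoner status, pregnancy and concurrent trials. Items addressing PET, polyester, allergy or material sensitivity: 0 of 15.

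2. **Is there a matching inclusion?** Section 4.2 has 7 top-level items: age, skeletal maturity, diagnosis, VAS, ODI, conservative treatment, and willingness with consent. Items requiring the absence of PET sensitivity: 0 of 7.

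3. **Does a general clause cover it?** No. Neither list refers back to 1.5, excludes patients with any contraindication to the device, or gives the investigator a discretionary exclusion. The one mention of contraindication in 4.3 concerns metabolic bone disease and spinal instrumentation, not the mesh material.

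4. **Does another entry condition cover it?** The definition of Enrolled in 11.0 adds completed consent, an assigned surgery date and expected insurance precertification. None of these concerns the device material.

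5. **What follows for a patient with known PET sensitivity who meets 4.2 and none of 4.3?** Under 4.0 and 4.1 the patient is eligible. Under 5.3.1 the patient may be enrolled and treated. Under 3.2.11, once enrolled, the patient is to receive the mesh. Under 1.5 the mesh is contraindicated. Read literally, the entry and treatment rules lead to the result that 1.5 rules out.

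6. **Would the trial's own checks catch it?** Section 12.0 gives enrolment outside the entrance criteria as one example of a major deviation, and 16.0 lists entrance criteria and inclusion deviations among its risk indicators. This patient breaches no listed criterion, so a check confined to those criteria would not flag the case. The general definition of a major deviation in 12.0 includes departures from the protocol that affect participant safety. Implanting against 1.5 could meet that definition, provided someone notices it.

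7. **Size.** The documents give no frequency of known PET sensitivity, so no expected count is calculated. The effect on the endpoint can be bounded per subject. If one subject who would otherwise have succeeded failed for this reason, the observed success proportion would fall by 1/102 = 0.98 percentage points with all 102 planned subjects, or 1/87 = 1.15 points with 87. The design inputs (55% performance goal, 68% assumed success, one-sided alpha 0.05, 80% power) do not change.

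**The case against.** The strongest reply is that 1.5 is itself part of the protocol. Investigators must follow the protocol (14.0), only trained investigators may use the device (1.4), and formal surgeon training is a listed risk-minimization measure (7.3). The contraindication concerns a known sensitivity, and a surgeon who has read 1.5 would not proceed. On this view 4.3 is silent rather than contradictory, and the wording in 5.3.1 permits treatment without overriding a prohibition stated elsewhere.

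Much of this stands, and it rules out several stronger readings:

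- A reader might infer that treating such a patient would be no protocol deviation at all. It would conflict with 1.5 and could be a major deviation under 12.0. The narrower statement is that it would not be an entrance-criteria deviation. Section 16.0 also lists procedure deviations and adverse events as indicators, so monitoring as a whole is not blind to it.
- A reader might extend the point to the allograft trace substances. Section 1.5 attaches only a caution to these, which leaves the matter to judgement, and nothing in 4.3 conflicts with that.
- A reader might conclude that the checklist and baseline form lack an allergy question. The sample forms, labeling and Surgical Technique Manual are appendices not available here, so this cannot be said. Section 10.0 shows only that the checklist is meant to screen for the entrance criteria.
- A reader might assume a prevalence and quote a chance of at least one affected subject. No prevalence is given, and such a figure would also assume that every surgeon disregards 1.5.

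What the reply does not remove is the mismatch in step 5. The text does not say that training covers contraindications, and an entry safeguard should not depend on recalling a background section when 4.1 tells the investigator to decide on the listed criteria.

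**Conclusion.** The point holds as an internal inconsistency with a safety consequence. A patient with the only contraindication stated for the mesh can satisfy every entrance criterion, and 3.2.11 then assigns that patient the device. Implantation would still conflict with 1.5, but a check against the entrance criteria alone would not show it.

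The number affected is probably very small, though the documents give nothing from which to estimate it. Alpha, power, sample size and the primary test are unaffected. The point merits a low-cost correction and is not a threat to the trial's validity. The conclusion rests on the protocol body as supplied; an appendix could contain a further safeguard, but the body text would still need to agree with itself.

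**What to change.** Reconcile 1.5 with 4.3, 3.2.11 and 5.3.1, so that the contraindication the protocol already states is reflected consistently in the entrance criteria and in the Inclusion/Exclusion checklist built from them. This calls for no new clinical rule, only agreement among passages that already exist. A departure would then also register as an entrance-criteria deviation under 12.0 and 16.0.

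The cost is about one line of protocol text with the matching checklist entry, and possibly a very rare candidate screened out. No statistical section needs to change.

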2.0 PURPOSE AND INVESTIGATION OBJECTIVES

2.1 PURPOSE

The purpose of this investigation is to evaluate the safety and effectiveness of the Spineology Interbody Fusion System in an instrumented lumbar interbody fusion.

2.2 INVESTIGATION OBJECTIVES

The primary objective of this investigation is to demonstrate the effectiveness of the SIFS in a lumbar interbody application. Effectiveness will be determined as a composite score that represents patient success. To be considered a patient success, each of the following criteria must be met at the 24-month study interval:

- Pain – Improvement in low back pain score evidenced by a 20 mm reduction on a 100 mm Visual Analog Scale (VAS) when compared to baseline (Note: a lower VAS pain score indicates less pain),
- Function – Improvement in low back function evidenced by a 15 point decrease of the Oswestry Disability Index (ODI) score compared to baseline. (Note: a higher ODI score indicates a greater disability with respect to low back function),
- Fusion – Bridging bone demonstrated on CT Scan
- Safety – Freedom from device-related Serious Adverse Events and secondary surgical interventions at the index level through the 24-month study interval.

In addition to the above stated primary objective, this investigation will yield data on the following outcomes, subject parameters and clinical utility:

- Variable scores over time (pain, function, fusion) as individual parameters
- Adverse Event rate(s) reported by relatedness and severity
- Neurological status over time
- Quantitative/qualitative radiographic data over time specific to the index level and contiguous levels (translation, angulation, disc height, and device position)
- Demographics
- Hospitalization Utility (duration of surgery, estimated blood loss and duration of hospitalization)
- Work status over time
- Pain medication use

Data collection is not limited to the above data points. Additional parameters will be reported on as appropriate. For a more detailed list of supplemental outcomes refer to Section 3.2 Scientific Soundness and Statistical Analysis.

